Vital signs	X	bid	bid	bid	bid	bid	bid	bid	bid	bid	bid

Phase Day	Screening 0	Treatment Phase			Follow-up Phase ^a							
		1	2	3 to 6 ^b	7 ^c (+2 days)	8 to 9	10 (+2days)	11 to 13	14 (+2 days)	15 to 27	28 (±2 days) EoS	
Study Procedure^d												
Nasal Swabs ^q												
Mid-turbinate nasal swab (if non-intubated) or endotracheal sample (if intubated): RSV diagnosis confirmation, viral and bacterial coinfection ^r	X											
Mid-turbinate nasal swab (if non-intubated) or mid-turbinate nasal swab and endotracheal sample (if intubated): RSV viral load, viral resistance (genome sequencing), biomarker, and infectious RSV viral load (plaque assay) ^s		X ^t	X	X	X		X		X			X
Clinical Laboratory Assessments												
Blood sampling for hematology ^u	X		X		X				X			
Blood sampling for biochemistry ^u	X				X				X			X
Urinalysis ^v	X			X					X			
Pharmacokinetics ^q												
Blood sampling for pharmacokinetics	Day 1 to Day 2											
		Post Dose 1	Post Dose 2									
		0.25 - 2h	0.5 - 1h 7h (±4)									
Group X ^w :		X	(X) ^x		X							
Group Y ^w :		X		(X) ^x	X							
Ongoing Subject Review												
Prior and Concomitant therapy	X	X	X	X	X	X	X	X	X	X	X	X
Adverse events	X	X	X	X	X	X	X	X	X	X	X	X

Abbreviations: bid: twice daily; ECG: electrocardiogram; eCOA: electronic clinical outcome assessment; eCRF: electronic case report form; EoS: end of study; IDMC: Independent Data Monitoring Committee; LD: loading dose; MD: maintenance dose; PK: pharmacokinetic(s); Q4h: every 4 hours; Q8h: every 8 hours; RSV: respiratory syncytial virus; SpO₂: peripheral capillary oxygen saturation.

Footnotes:

- a. If a subject is discontinued from study drug, a follow-up visit will be scheduled 2 days (+2 days), 5 days (+2 days), 9 days (+2 days), and 23 days (± 2 days) after the last dose of study drug was administered. Assessments should be performed as indicated in the Time and Events Schedule, respectively for the Day 7, Day 10, Day 14, and Day 28 visit.
- b. The subject may be discharged after Day 2 study procedures, but may also remain hospitalized if deemed appropriate by the investigator. Hospitalization duration will not be extended solely for study purposes.
- c. If treatment duration is increased to up to 10 days, then all assessments performed on Day 7 will again be performed 1 day (+2 days) after administration of the last MD.

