- If the IDMC considers an event or multiple events to represent an unacceptable risk to the health and well-being of subjects at that or higher dose levels.

Withdrawal From the Study

Each parent/caregiver has the right to withdraw the subject at any time for whatever reason without affecting the right to treatment by the investigator. The investigator should make an attempt to contact the parent(s)/caregiver(s) of subjects who did not return for scheduled visits or follow-up. Although the subject's parent(s)/caregiver(s) are not obliged to give reason(s) for withdrawing early, the investigator should make a reasonable effort to ascertain the reason(s) while fully respecting the subject's rights.

A subject will be withdrawn from the study for any of the following reasons:

- Lost to follow-up.
- Withdrawal of consent.
- Death.
- The subject's parent(s)/caregiver(s) is poorly compliant with study procedures, study drug administration, visits, and assessments, after evaluation and discussion between the investigator and the sponsor.
- Decision by the sponsor to stop or cancel the study.
- Decision by the investigator to withdraw subjects.
- Decision by local regulatory authorities and Independent Ethics Committee (IEC)/Institutional Review Board (IRB) to stop or cancel the study.

If parent(s)/caregiver(s) withdraw the subject from the study before the end of the treatment phase, the subject's parent(s)/caregiver(s) will be encouraged to continue with end-of-treatment and follow-up assessments in accordance with the [Time and Events Schedules](#).

If a subject is lost to follow-up, every reasonable effort must be made by the investigator/study-site personnel to contact the parent(s)/caregiver(s) and determine the reason for discontinuation/withdrawal. The measures taken to follow up must be documented.

When a subject is withdrawn by his/her parent(s)/caregiver(s) before completing the study, the reason for withdrawal is to be documented in the eCRF and in the source document. Study drug assigned to the withdrawn subject may not be assigned to another subject. Subjects who have withdrawn before all RSV mid-turbinate nasal swabs (for RSV viral load) or PK samples have been taken may be replaced. If a subject withdraws from the study before the end of the treatment phase, end-of-treatment and follow-up assessments should be obtained, unless the reason for withdrawal was withdrawal of consent.

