Subjects who are admitted to hospital due to RSV infection, including those who are otherwise healthy and those with underlying comorbidities (prematurity at birth [subject's gestational age was <37 weeks; for infants <1 year old at randomization], bronchopulmonary dysplasia, congenital heart disease, other congenital diseases, Down syndrome, neuromuscular impairment, or cystic fibrosis) can participate. However, enrollment of subjects with comorbidities can only start after at least 9 subjects have completed treatment with the 60 mg/kg LD/40 mg/kg MD lumicitabine regimen, after their safety and PK data have been reviewed by the IDMC, and after the IDMC has recommended that the recruitment of subjects with underlying comorbidities may start. Screening should be completed as soon as possible and the subject randomized within ≤ 5 days of RSV symptom onset. Procedures that are standard of care and performed within approximately 72 hours prior to randomization may be used in determining study eligibility or determining baseline values.

Randomization will be stratified by duration of RSV symptoms from onset until time of randomization (≤ 3 days; >3 days to ≤ 5 days), and by presence or absence of at least 1 comorbid condition for severe RSV disease (prematurity at birth [subject's gestational age was <37 weeks; for infants <1 year old at randomization], bronchopulmonary dysplasia, congenital heart disease, other congenital diseases, Down syndrome, neuromuscular impairment, or cystic fibrosis).

Treatment with lumicitabine should be initiated as soon as possible but no later than 4 hours after randomization to maximize the opportunity for the compound to inhibit viral replication and potentially improve outcomes. The parent(s)/caregiver(s) will administer the study drug at home until all doses are administered if the subject is discharged prior to the completion of treatment. Subjects will be evaluated for a total of 28 days postrandomization. Depending on the discharge date, assessments will be completed either in the hospital or during outpatient visits. On Day 28,

all subjects will complete the study either as an inpatient or outpatient. The total study duration for each subject will be 28 days, screening phase not included.

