5.3.1.3. RSV clinical outcome

Measurement	Formula
Length of hospital stay (hours) [Time-to event]	
The time from treatment initiation to hospital discharge (=event) in hours.
 
Subjects who complete or withdraw from the study prior to the event will be censored at the date of completion or withdrawal. If the time is not available they will be censored at 12:00. In case of death the subject will be censored at the maximum observed number of hours until the occurrence of the event or censoring for all subjects achieving the event or being censored because of study completion or withdrawal.
 
(Date and time of event or censoring - date and time of first dose of study drug)/3600, rounded to one decimal.

Time to readiness for discharge (hours) [Time-to event]	
The time from study treatment initiation to readiness for discharge (= event) in hours, with readiness for discharge defined by the investigator.
 
Derivation similar as “Length of hospital stay”

Length of hospital stay since hospital admission (hours) [Time-to event]	
The time from hospital admission to hospital discharge (= event) in hours.
 
Derivation of censoring similar as “Length of hospital stay”.
 
(Date and time of event or censoring - date and time of hospital admission)/3600, rounded to one decimal

Measurement	Formula
Time to readiness for discharge since hospital admission (hours) [Time-to event]	
The time from hospital admission to readiness for discharge (= event) in hours, with readiness for discharge defined by the investigator.
 
Derivation similar as “Length of hospital stay since hospital admission”

Duration of intensive care unit (ICU) stay (hours) [Duration]	
The total number of hours a subject stayed in ICU (= event) from first intake until study termination, calculated as sum of [(end date and time of event - start date and time of event)/3600], rounded to one decimal for all separate events per subject
 
If the initial start time is prior to the first dose of study drug, the duration prior to the first dose of study drug will be deducted from the overall duration.
 
If the end date is missing, the end date is considered to be after study completion or withdrawal. If the end date and time is after the study completion/discontinuation, the duration after the date and time of study completion/discontinuation will be deducted from the overall duration. If the time is not available it will be put at 12:00.

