Requirement for supplemental feeding/hydration	
Does the subject require supplemental feeding/hydration (e.g. IV catheter/nasogastric tube) after first dose of study drug?
 
Categories will be Yes (1) or No (0).
 
Only derive this parameter for subjects that didn't require supplemental feeding/hydration before first dose of study drug.

Time to end of intensive care	The time from first study drug intake until the time of

Measurement	Formula
unit (ICU) stay (hours) [Time-to event]	
discharge from the ICU after which the subject was not readmitted to the ICU (= event)
 
Subjects who complete or withdraw from the study prior to the event will be censored at the date of completion or withdrawal. If the time is not available they will be censored at 12:00. In case of death the subject will be censored at the maximum observed number of hours until the occurrence of the event or censoring for all subjects achieving the event or being censored because of study completion or withdrawal. If no admittance to the ICU was necessary, the value will be set to 0.
 
(Date and time of event or censoring - date and time of first dose of study drug)/3600, rounded to one decimal

Time to end of Oxygen supplementation (hours) [Time-to event]	
The time from first dose of study drug start of oxygen supplementation to the last end date and time of any oxygen supplementation (= event) in hours (Oxygen supplementation is indicated on the Oxygen Supplementation form: Type of supplemental oxygen administration.). (Note: it is not necessary that the subject started on oxygen at baseline.)
 
If the end date is missing, the end date is considered to be after study completion or withdrawal.
 
Subjects who complete or withdraw from the study prior to the event will be censored at the date of completion or withdrawal. If the time is not available they will be censored at 12:00. In case of death the subject will be censored at the maximum observed number of hours until the occurrence of the event or censoring for all subjects achieving the event or being censored because of study completion or withdrawal.
 
If no oxygen supplementation was necessary after first dose of study drug, the value will be set to 0 hours.
 
(Date and time of event or censoring - date and time of first dose of study drug)/3600, rounded to one decimal

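### A missing end date for ICU stay, oxygen, ventilation or supplemental feeding is carried to study end even when the child's hospital discharge is on record

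*SAP*

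**What the plan says.** The relevant rules are in the table of SAP 5.3.1.3.

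- **Duration of ICU stay.** The variable is defined as "The total number of hours a subject stayed in ICU (= event) from first intake until study termination", summed over separate ICU events. For an absent end date the row says: "If the end date is missing, the end date is considered to be after study completion or withdrawal". When the end falls after study completion or discontinuation, "the duration after the date and time of study completion/discontinuation will be deducted from the overall duration". Together these place the end of the stay at study end.
- **Time to end of oxygen supplementation.** The same missing-date sentence appears. A child who completes or withdraws before the event is censored at that date.
- **Time to end of non-invasive ventilation, invasive ventilation, and supplemental feeding/hydration.** Each row takes its derivation from the oxygen row.
- **Time to end of ICU stay.** The missing-date sentence does not appear in this row.
- **Length of hospital stay.** The event is discharge: "The time from treatment initiation to hospital discharge (=event) in hours". A discharge date and time is therefore already an analysis input.

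Follow-up continues well beyond discharge for many children. SAP 1.2.1 states: "The total study duration for each subject will be 28 days, screening phase not included". A footnote to the protocol's Time and Events Schedule states: "The subject may be discharged after Day 2 study procedures".

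**The concern.** A child who has left hospital is no longer in that hospital's ICU or on its ventilator. The missing-date rule does not look at the discharge record, so two variables in the same table can contradict each other for the same child: discharged on Day 5 in one, in the ICU to Day 28 in the other.

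Two things are at stake. ICU duration is a protocol secondary endpoint, summarised by arm on what is likely to be a skewed variable with few non-zero values, so a single record of this kind can visibly move an arm's mean and SD. For oxygen, ventilation and feeding, a date gap becomes a censored observation at study end, and the child enters the analysis as not yet weaned. SAP 5.3.2.3 compares these times with placebo by a stratified Gehan test and combines the p-values with those for requirement of support by Liptak's method. A censored oxygen or feeding component also censors time to clinical stability, which is analysed by Cox regression with logrank and Gehan-Wilcoxon tests.

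**Working it through.** The plan gives no figure for ICU duration, so there is nothing to reproduce. The check applies the written rule to an example child.

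**Inputs**
- Study end: Day 28, window ±2 days (protocol Time and Events Schedule), with Day 1 the day of first dose (SAP 2.5).
- Arm size: 60 planned per regimen (SAP 1.2.1). An expected ITT-i set of 120 (SAP 5.1.1) gives 120 / 3 = 40 at 1:1:1.
- Assumed: the child is in the ICU at first dose, completes follow-up and has no ICU end date. Discharge on Day 3, 5 or 7 is chosen for illustration. Differences in clock time within a day are ignored.

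**Hours counted under the rule** = (study-end day − 1) × 24
- Day 28: 27 × 24 = 648 h
- Day 26: 25 × 24 = 600 h
- Day 30: 29 × 24 = 696 h

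**Upper bound from the discharge record** = (discharge day − 1) × 24. **Excess** = hours counted − upper bound. **Shift in arm mean** = excess / n. With study end on Day 28:

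| Discharge | Upper bound | Counted | Excess | Mean shift, n = 60 | Mean shift, n = 40 |
|---|---|---|---|---|---|
| Day 3 | 48 h | 648 h | 600 h | 10.0 h | 15.0 h |
| Day 5 | 96 h | 648 h | 552 h | 9.2 h | 13.8 h |
| Day 7 | 144 h | 648 h | 504 h | 8.4 h | 12.6 h |

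For the Day 5 child, 552 / 24 = 23 days, or 552 / 168 = 3.3 weeks. Over the visit window the excess runs from 600 − 96 = 504 h to 696 − 96 = 600 h. It is measured against the discharge bound, so it is larger if the child left the ICU before leaving hospital.

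SAP 5.3.2.3 also summarises ICU duration by whether the child was in the ICU at first dose. The documents do not give the size of that subgroup. If it were 4 to 12 children in an arm (assumed), one such record would shift its mean by 552 / 4 = 138 h down to 552 / 12 = 46 h.

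**Oxygen, ventilation and feeding.** No hours are added here. Under the rule the example child has no event and is censored at about 648 h. Under a discharge cap the child has an event no later than 96 h. In a Gehan-type comparison the first version ranks the child as outlasting every child weaned before study end; the second does not. The effect on the p-value depends on how many such records each arm has, which cannot be known from the documents.

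**The case against.** Several objections have force.

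- **The gap may not survive cleaning.** A discharged child with an open ICU record is an obvious inconsistency, and the protocol provides for queries and verification (sections 17.5, 17.7, 17.9). Reading an open end date as ongoing also matches the SAP's convention for medications (4.6). This limits how often the rule would bite, but the rule exists for dates that remain missing, and there it gives an impossible answer when the discharge date contradicts it.
- **ICU duration is descriptive and medians are planned.** Both are true (SAP 5.3.2 and 5.3.2.3). The median resists one stray record, so no request for medians is needed. The mean, SD and confidence interval are reported too and are not protected.
- **Readmission.** A child can be in the ICU after a first discharge: ICU events are summed and SAP 8.1 lists the ICU as a readmission type. A cap at an unspecified discharge could produce a negative duration. This stands, and the cap must name the discharge closing the admission in question.

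A reader might go further and infer that ICU duration needs a death rule because its row has none, or that deaths bias it in the drug's favour. The documents do not support that. The variable counts hours actually spent in the ICU, and a child who dies after 24 h spent 24 h there. Time to end of ICU stay, which carries the comparison with placebo, does have a rule: "In case of death the subject will be censored at the maximum observed number of hours". Mortality is analysed separately. Any effect of a death on mean ICU duration depends on its arm and timing; a death in the ICU on Day 21, after a stay from first dose, would count 20 × 24 = 480 h.

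**Conclusion.** The point holds as a minor defect in a derivation rule. An unresolved missing end date overrides a recorded discharge. In ICU duration this counts about 648 h for a child in the ICU from first dose and discharged at 96 h, an excess of about 552 h. One such child shifts the arm mean by 9.2 h (n = 60) or 13.8 h (n = 40), with little effect on the median. For oxygen, ventilation and feeding the consequence is wrong censoring, which reaches tested comparisons and clinical stability.

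The figures assume ICU care from first dose and full follow-up. A later ICU admission or an early withdrawal makes the excess smaller. It is tempting to say that a gap adds four weeks, but 648 h (3.9 weeks) is the total counted, and the part added in this example is 3.3 weeks. It is also tempting to extend the point to time to end of ICU stay, but that row does not contain the missing-date sentence. The numbers of missing dates and ICU admissions are not given, so neither the overall size nor the direction of bias between arms can be stated.

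**What to change.** Replace the missing-date sentence in the ICU duration and oxygen rows, and let the ventilation and feeding/hydration rows inherit the change:

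- If an end date is still missing after query and the discharge closing that admission is recorded, set the end of ICU stay and of invasive ventilation to that discharge date and time.
- Do the same for oxygen, non-invasive ventilation and supplemental feeding/hydration, unless use at home is recorded. Protocol section 8 already has home oxygen recorded as a therapy.
- Treat the stay or support as ongoing at completion or withdrawal only when no such discharge exists or the record is marked ongoing.

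The cost is a few sentences in the SAP, using dates already collected, to be settled before unblinding. The drawback is a slight overstatement of support time for children moved to a ward or weaned before discharge. That overstatement is bounded by the hospital stay, which the current rule's is not.
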